6.4 Interventions

6.4.1 Arm A (Intervention)

6.4.1.1 iACT4CARERS plus TAU

The iACT4CARERS intervention (https://iact4carers.com), which has been tested in our previous feasibility study will be used. iACT4CARERS will be delivered in addition to TAU as described in ARM B. iACT4CARERS consists of eight online sessions. Each session has three phases: self-learning,

reflection and practice. The self-learning phase will guide participants through core ACT skills (OPEN, AWARE and ENGAGED) that together constitute psychological flexibility. Interactive exercises to illustrate ACT skills will be presented using multiple modes (video/audio/text). The reflection phase encourages participants to reflect on learned skills and leave questions for their trial therapist if anything is unclear. Trial therapists will provide individually tailored written feedback to validate and normalise difficult thoughts and emotions participants are experiencing and encourage them to practice ACT skills they found helpful. The practice phase allows participants to set a goal and practice ACT skills offline between online sessions.

In addition to online sessions, two 30-min one-to-one sessions via telephone or video call will be offered to each participant by their trial therapist. These one-to-one sessions can be booked anytime while completing iACT4CARERS, but participants will be encouraged to book the first session at the start of the programme and the second session a few weeks after this. These sessions will focus on encouraging participants to: (1) express their feelings and emotional needs; (2) share their challenges and concerns regarding the use of technology; and (3) discuss the expectation for weekly reflection and online feedback from their trial therapist so that support can be tailored. These one-to-one sessions are optional and not signing up for these will not result in the withdrawal from iACT4CARERS.

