6.4.2.2 Treatment Schedule

Participants will continue to receive any routine support over 12 weeks. They will receive no contact with trial therapists as described in ARM A.

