6.4.3 Compliance and Adherence

To improve adherence to the intervention, the iACT4CARERS software will monitor participant progress. The iACT4CARERS software sends automatic multiple text/email reminders to participants

to prompt them to continue with the intervention (e.g. no completion of the session for 5 days, 10 days and 14 days). The iACT4CARERS software will also monitor therapist engagement and send automatic text/email reminders to therapists if they have not provided online feedback for a certain period (e.g. no feedback provided for 7 days, 10 days and 14 days). Both text and email reminders will be used to improve adherence, but participants have an option to unsubscribe from email reminders if they only wish to receive text reminders. If no actions are taken following multiple attempts, the unblinded Trial Manager or delegate at NCTU will make a follow-up phone call.

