6.6.1.2 Intervention

The eligibility criteria will be fully checked within a week from the completion of baseline assessments, and eligible participants will be randomised to iACT4CARERS plus TAU or TAU alone by NCTU. Participants randomised to iACT4CARERS plus TAU will receive a link to the iACT4CARERS website and login details from the unblinded Trial Manager based at NCTU via email (and post if requested). Unauthorised access to the intervention will be prevented by providing participants with unique login details. The allocated trial therapist will also receive a notification from the unblinded Trial Manager based at NCTU via email.

6.6.1.2 12-week and 24-week Follow-Ups

Twelve and twenty-four weeks after randomisation, participants will receive an email to ask them to complete the follow-up measure online from NCTU, if they have requested this. The email will include a reminder, which reiterates the reasons why this follow-up data is important. If the follow-up measure is not completed within a week, the Research Associate based at UEA who is blind to treatment allocation will be informed by NCTU and will give a follow-up phone call to check if the participant needs additional support for completing the online assessments. If the participant

decides not to complete the assessments, the Research Associate will ask them to provide a reason if possible. Participants, who have indicated that they wish to receive the follow-up measure via post, will receive the follow-up assessments via post from NCTU and will be asked to return them to NCTU using a prepaid envelope. The unblinded Trial Manager based at NCTU will give a follow-up phone call a week after the assessments have been posted to ensure that participants have received the follow-up measure and check if additional support is needed for completion. The unblinded Trial Manager based at NCTU will manually enter the data into the central database upon the receipt of documents. Participants will be asked not to reveal their allocation to the blinded Research Associate during follow-up calls.

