Selected participants from the intervention arm will be invited to an individual interview at a 12week follow-up as part of the process evaluation. The interview is optional, and participants will receive a separate PIS and consent form for this part of the study if invited. Interviews will be conducted by the unblinded delegate based at NCTU via video call or telephone. Trial therapists and referrers will also be invited to interviews (see 6.5.3 Qualitative Study/Process Evaluation). If the interview is conducted by video call, the sound recording of the interview through the video conference software will be used to audio record the session. If the interview is conducted by telephone, a digital voice recorder will be used. An audio file of interview will be uploaded to a secure server at UEA immediately after the interview, and the original recording will be completely deleted from the software or voice recorder. The recording will be transcribed as soon as possible using software approved by UEA (e.g. EDCaption) or the external transcribing company. The audio files uploaded to the secure server at UEA will be deleted as soon as the accuracy of the transcripts has been confirmed.

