6.11.3 Data Monitoring for Harm

6.11.3.1 Safety reporting

Definitions of harm of the EU Directive 2001/20/EC Article 2 based on the principles of ICH GCP apply to this trial.

This is a low-risk intervention. No specific risks, or adverse events were reported during feasibility testing of the intervention[22]. Any non-serious untoward incidents occurring during this trial (e.g. clear evidence of high levels of distress making participants difficult to continue with the study) will be recorded in an incident report form which will be monitored for frequency and severity. The participant's GP will also be informed to contact NCTU if they become aware of any adverse event during the study such as significant deterioration in mental health and they feel that the participant should no longer be taking part in the study. Serious adverse events (SAE) will be collected using an SAE form.

Table 3: Serious Adverse Event Definitions

Serious Adverse Event (SAE)	Any adverse event that:
	 results in death; is life threatening*; requires hospitalisation or prolongs existing hospitalisation**; results in persistent or significant disability or incapacity.
	The most likely SAE to occur in this study is new reports of active suicidal ideation with active suicidal behaviours/plans and imminent intent.

* The term life threatening here refers to an event in which the patient is at risk of death at the time of the event; it does not refer to an event that might hypothetically cause death if it was more severe (e.g. a silent myocardial infarction).

** Hospitalisation is defined as an in-patient admission, regardless of length of stay, even if the hospitalisation is a precautionary measure for continued observation. Hospitalisation for preexisting conditions (including elective procedures that have not worsened) do not constitute an SAE.

Serious adverse events do NOT include:

- Pre-existing disease or a physical health condition present before trial treatment;
- An exacerbation of such pre-existing physical illness (e.g. cancer) during the trial;
- A physical health condition that is detected after trial treatment.

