6.11.3.6 Notifications

6.11.3.6.1 Notifications by the Investigator to NCTU

NCTU must be notified of all SAEs within one working day of a responsible individual (Research Associate or trial therapist) becoming aware of the event. The responsible individual should notify NCTU of any SAEs occurring from the time of randomisation until the last follow-up assessment.

The SAE form must be completed by the responsible individual (Research Associate or trial therapist) with attention paid to the causality and expectedness of the event. The responsible investigator (the Chief Investigator for Research Associates and the Principal Investigator for trial therapists) should check the SAE form at the earliest opportunity, make any changes necessary, sign and then email to the Trial Manager at NCTU within one working day for review.

The Trial Manager will review the SAE form and disseminate to the Chief Investigator and sponsor representative within 72 hours of being informed to assess relatedness. The Trial Manager will enter the report into the database. The DMEC will be informed of SAEs by the Trial Manager periodically unless the Chief Investigator or sponsor representative escalates the SAE or deems necessary. This is a non-CTIMP study and only SAEs that are related and unexpected will be reported to REC within 15 days of the Chief Investigator becoming aware of the event.

The minimum criteria required for reporting an SAE are the trial number and date of birth, name of reporting investigator and sufficient information on the event to confirm seriousness. Any further information regarding the event that is unavailable at the time of the first report should be sent as soon as it becomes available.

Follow-up SAE forms (clearly marked as follow-up) should be completed and emailed to NCTU, as per above procedure. Additional information and/or copies of test results etc may be provided separately. The participant must be identified by trial number, date of birth and initials only. The participant's name should not be used on any correspondence and should not be used on any correspondence.

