7.6 Safety data

Safety data (adverse events reported from time of first exposure to treatment to end of treatment) will be summarised by group. Any serious adverse events will be described in full including possible relationship to the treatment.

Serious adverse events related or unrelated to the intervention, will be analysed using a logistic regression model with the random effects, pre-specified prognostic variables and treatment group as explanatory variables.

8. Description of Tables and Figures

All data up to the time of study completion/withdrawal from the study will be included in the analysis, regardless of duration of treatment.

All raw data will be presented to the original number of decimal places. The mean and standard deviation will be presented with to 2 decimal places or 3 significant figures depending upon the nature of the data. Percentages will be presented in to 1 decimal place. All categories of variables will be presented even if there is no data. Blank cells, were data are not expected, will be filled by "-" in reporting of results.

Precision of p-values will be 3 decimal places, i.e. p-values less than 0.001 will be presented as <0.001 and if equal to 1 then \ge 0.999.

9. Software

All analysis will be performed using SAS[®] Software version 9.4 and Stata version 17.

10. References

- 1. Collins, R. and N. Kishita, *Prevalence of depression and burden among informal caregivers of people with dementia: A meta-analysis.* Ageing and Society, 2020. **40**(11): p. 2355-2392.
- 2. Kaddour, L. and N. Kishita, *Anxiety in informal dementia caregivers: a meta-analysis of prevalence.* Journal of Geriatric Psychiatry and Neurology, 2020. **33**(3): p. 161-172.
- 3. McManus, S., et al., eds. *Mental health and wellbeing in England: Adult psychiatric morbidity survey 2014*. 2016, NHS Digital: Leeds, UK.
- 4. National Institute for Health and Care Excellence, *NICE guideline [NG97] Dementia: assessment, management and support for people living with dementia and their carers*. 2018, NICE: London, UK.
- 5. Alzheimer's Society, *Dementia 2014: Opportunity for change*. 2014, Alzheimer's Society: London, UK.
- 6. A-Tjak, J.G.L., et al., A meta-analysis of the efficacy of acceptance and commitment therapy for clinically relevant mental and physical health problems. Psychotherapy and Psychosomatics, 2015. **84**(1): p. 30-36.

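### Therapists give the intervention arm an extra route for SAE detection, and no scheduled adverse-event question is described for either arm, so the planned between-arm SAE model is open to detection bias

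*Protocol*

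**What the plan says.** **Who reports.** Protocol 6.11.3.6.1: "NCTU must be notified of all SAEs within one working day of a responsible individual (Research Associate or trial therapist) becoming aware of the event". Sections 6.11.3.5.1 and 6.11.3.5.3 give the same two roles the first assessment of seriousness and causality.

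**Who has a therapist.** In the intervention arm therapists give written feedback on up to eight online sessions, and "two 30-min one-to-one sessions via telephone or video call will be offered to each participant by their trial therapist" (6.4.1.1; these calls are optional). For TAU participants, 6.4.2.2 states: "They will receive no contact with trial therapists as described in ARM A".

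**Other contact in the intervention arm only.** If reminders fail, "the unblinded Trial Manager or delegate at NCTU will make a follow-up phone call" (6.4.3). At 12 weeks, "Selected participants from the intervention arm will be invited to an individual interview" (6.6.1.2).

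**Follow-up in both arms.** Outcomes are self-completed. For online participants, section 6.6.1.2 (12-week and 24-week Follow-Ups) reads: "If the follow-up measure is not completed within a week, the Research Associate based at UEA who is blind to treatment allocation" is told by NCTU and telephones to offer help with completion. Table 2 has no adverse-event row.

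**What is expected and how it is analysed.** Protocol 6.11.3.1: "The most likely SAE to occur in this study is new reports of active suicidal ideation", with suicidal behaviours or plans and imminent intent. Protocol 6.5.2 lists SAEs among the secondary outcomes and records those that are reported. SAP 7.6: "Serious adverse events related or unrelated to the intervention, will be analysed using a logistic regression model", with treatment group as an explanatory variable. Neither document mentions unequal detection.

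**The concern.** Events are captured when someone in contact with the participant learns of them, and one arm has more such contact by design. A treatment-group coefficient for SAEs would then reflect contact intensity as well as harm. With equal true risk, the intervention could appear to cause SAEs. A true reduction could be partly or wholly masked.

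The event named as most likely, new active suicidal ideation with intent, depends heavily on disclosure to another person. The only suicide risk assessment described is the one at screening (Protocol 6.3.1.3).

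The primary outcome is not affected. The published harm comparison is.

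**Working it through.** **1. The plan's own figures.** The documents give no SAE risk, detection rate or power for the SAE comparison, so there is no stated figure to reproduce. The only number borrowed is the arm size. The sample-size calculation (d = 0.35, two-sided 5%, 90% power) solves to 172.5, so 173 per arm as stated. 173 / (1 − 0.30) = 247.1, so 248 per arm and 496 in total, also as stated.

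**2. Routes by which an SAE could become known.**

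| Route (Protocol section) | Intervention | TAU | Adverse-event enquiry described? |
|---|---|---|---|
| Therapist feedback, up to 8 sessions (6.4.1.1) | yes | no | no |
| Two optional therapist calls (6.4.1.1) | yes | no | no |
| Adherence call after failed reminders (6.4.3) | yes | no | no |
| 12-week interview, selected participants (6.6.1.2) | yes | no | no |
| Research Associate call if online form is late (6.6.1.2) | yes | yes | no, about completion |
| Trial Manager call to postal participants (6.6.1.2) | yes | yes | no, about receipt and completion |
| Contact before assessments (6.8.2) | yes | yes | no |
| GP notice (6.11.3.1) | yes | yes | spontaneous reporting |
| Modified CSRI and diary sheets (6.10.5) | yes | yes | service use; not named as an SAE source |

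Four routes exist in one arm only. None of the five common routes is described as a systematic SAE enquiry.

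**3. Illustration of size (assumed values).** Let p be the true SAE risk, equal in both arms, and s0 the detection probability in TAU. Access to the programme ends at 12 weeks (6.4.1.2), while SAEs are notifiable from randomisation to the last follow-up, at 24 weeks (6.11.3.6.1). Assume events spread evenly over 24 weeks, detection of 0.90 in the intervention arm to week 12, and s0 in both arms afterwards. Then:

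- average intervention detection s1 = (0.90 + s0) / 2
- recorded risks q1 = p × s1 and q0 = p × s0
- apparent OR = [q1 / (1 − q1)] / [q0 / (1 − q0)]
- expected recorded cases = 248 × q

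With p = 4%:

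| s0 | s1 | q1 v q0 | Expected cases, intervention v TAU | Apparent OR |
|---|---|---|---|---|
| 0.75 | 0.825 | 0.033 v 0.030 | 8.2 v 7.4 | 1.10 |
| 0.50 | 0.70 | 0.028 v 0.020 | 6.9 v 5.0 | 1.41 |
| 0.30 | 0.60 | 0.024 v 0.012 | 6.0 v 3.0 | 2.02 |

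The result hardly depends on p. For s0 = 0.30, p = 2% gives (0.012/0.988) / (0.006/0.994) = 2.01, and p = 8% gives (0.048/0.952) / (0.024/0.976) = 2.05.

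**4. Chance of a false signal (a second set of assumed values).** Take p = 5% and s0 = 0.5, and let therapists pick up half of what the other routes miss in the first 12 weeks. Averaged over 24 weeks the extra detection is 0.25, so s1 = 1 − 0.5 × 0.75 = 0.625 and the apparent risk ratio is 0.625 / 0.5 = 1.25. Expected cases are 7.8 v 6.2. Exact binomial enumeration with 248 per arm and an uncorrected two-sided 5% chi-square test, standing in for the planned logistic model, gives significance in 7.0% of trials (6.1% towards an intervention excess). With equal detection the figure is 4.9%.

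**5. Near-complete common detection.** If s0 = 0.9 and therapists made early detection perfect, s1 = (1 + 0.9) / 2 = 0.95 and the risk ratio is 0.95 / 0.9 = 1.06.

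**6. After the fix.** Restricting the comparison to common sources sets s1 = s0, so the apparent ratio is 1.00 provided response is similar by arm. The same enumeration gives false-signal rates of 2.9% to 5.1% for p of 2% to 10% and s0 of 0.3 to 0.9.

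**The case against.** The strongest reply is that detection is not confined to therapists. Research Associates and GPs cover both arms. The modified CSRI collects service use from everyone at 12 and 24 weeks, supported by diary sheets, and hospital admission is one of the Table 3 criteria. Every postal participant gets a call, and contact before assessments is planned. Therapists are not described as asking about adverse events either, and their two calls are optional. All of this stands. It limits the point to an additional channel in one arm and leaves the size unknown. It does not remove the asymmetry: the GP route relies on spontaneous reporting and is worded around the GP feeling that the participant should stop taking part, and the CSRI is not linked to SAE reporting anywhere.

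Three stronger readings are tempting, and the documents do not support them.

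- *That participants are never asked about adverse events.* Table 2 is not an exhaustive list of items. It also omits the follow-up question on death of the person with dementia (Protocol 6.4.5). The case report forms are not in the documents, so one can say only that no such item is described.
- *That TAU participants have no contact before week 12 against ten contacts in the other arm.* Ten is a ceiling, and a zero ignores the contact planned before assessments.
- *That the early detection gap applies to all 24 weeks.* With the values in step 3 of the working, that would give odds ratios of about 1.2, 1.8 and 3.1, but programme access ends at 12 weeks.

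The SAP's adverse-event window (first exposure to end of treatment) also differs from the protocol's SAE window. That is a separate matter, and aligning the two would not equalise detection.

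**Conclusion.** The point holds in limited form. As the plan is written, the SAP 7.6 comparison is open to detection bias, because therapist contact adds a reporting channel in one arm and no even-handed enquiry is described to offset it. The expected direction is towards more recorded SAEs with the intervention. A reader might infer that the comparison is shown to be biased by a known amount. It is not: every risk and detection rate used above is an assumption. The apparent odds ratio runs from about 1.1 to 2.0 over TAU detection of 75% to 30%, and the distortion is slight if common detection is near 90%. The matter deserves correction because SAEs are a secondary outcome with a planned model and the remedy is cheap.

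**What to change.** 1. Add to the 12- and 24-week follow-up measure, identically in both arms, a short dated question on hospital admission and the other non-fatal Table 3 criteria, including the event named as most likely. Add the row to Table 2 and route positive answers through the existing SAE pathway. If the form already has such an item, show it in Table 2 and name it in SAP 7.6. Check hospital admissions in both arms against the modified CSRI.
2. Record the source of each SAE. In SAP 7.6, base the between-arm comparison on sources common to both arms: the identical questions, admissions identified from the CSRI, and deaths from any source. Deaths must be kept in from all sources because participants cannot self-report them. Report the number of responders by arm. List events known only through therapist or other intervention-only contact separately and descriptively.
3. If the forms can no longer be changed, replace the between-arm test with descriptive reporting by arm and source, and state the detection limitation. This may be the practical option, since SAP 7.2 describes site reallocation of self-referred participants in the past tense.

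**Cost.** A protocol amendment, a few items on an existing form, a source field and SAP wording. The questionnaire becomes slightly longer and relies on 12-week recall. Non-responders are missed (the plan assumes 30% dropout), which could itself differ by arm. Positive answers need prompt review to meet the one-working-day rule.

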6.11.3.6.2 NCTU responsibilities

Medically qualified staff at NCTU and/or the Chief Investigator will review all SAE reports received. In the event of disagreement between the causality assessment given by the Principal Investigator and the Chief Investigator, both opinions and any justifications will be provided in subsequent reports.

NCTU will keep investigators informed of any safety issues that arise during the course of the trial. NCTU will also submit annual reports to the REC.

6.11.4 Quality Assurance and Control

6.11.4.1 Risk Assessment

The Quality Assurance (QA) and Quality Control (QC) considerations for the iACT4CARERS trial are based on the standard NCTU Quality Management Policy that includes a formal Risk Assessment, and that acknowledges the risks associated with the conduct of the trial and proposals of how to mitigate them through appropriate QA and QC processes. Risks are defined in terms of their impact on: the rights and safety of participants; project concept including trial design, reliability of results and institutional risk; project management; and other considerations.

QA is defined as all the planned and systematic actions established to ensure the trial is performed and data generated, documented and/or recorded and reported in compliance with the principles of

GCP and applicable regulatory requirements. QC is defined as the operational techniques and activities performed within the QA system to verify that the requirements for quality of the trial related activities are fulfilled.

